### **8.2 Secondary Objectives**

The secondary objectives of the study are to:

1. Compare difference in PFS rate at 4 months (PFS-4m) between the 2 treatment arms per IIR
2. Compare difference in PFS rate at 1 year (PFS-1y) between the 2 treatment arms per IIR
3. Compare difference in OS and OS rate at 1 year (OS-1y) between the 2 treatment arms
4. Compare difference in objective response rate at 4 months (ORR-4m) between the 2 treatment arms per IIR
5. Compare difference in objective response rate (ORR) between the 2 treatment arms per IIR
6. Compare difference in safety and tolerability between the 2 treatment arms
7. Characterize the pharmacokinetics (PK) of lenvatinib, when administered in combination with ifosfamide and etoposide
8. Compare difference in health-related quality of life (HRQoL) as assessed by using the Pediatric Quality of Life Inventory (PedsQL) Generic Core Scales and Cancer Module between the 2 treatment arms
9. Assess the palatability and acceptability of the suspension formulation of lenvatinib in subjects receiving the suspension formulation in the study

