**Test Arm (Arm A): Lenvatinib + Ifosfamide + Etoposide**

Lenvatinib 14 mg/m^2, orally administered once daily in each 21-day cycle.

Lenvatinib is provided as hard capsules containing 1 mg, 4 mg, or 10 mg lenvatinib. An extemporaneous suspension of lenvatinib capsules should be used for subjects unable to swallow capsules. After adjustment for body surface area (BSA), the daily dose cannot exceed 24 mg QD.

Ifosfamide 3000 mg/m^2/day, IV, for 3 consecutive days (Day 1 to 3), every 21 days, for a maximum of 5 cycles.

Etoposide 100 mg/m^2/day, IV, for 3 consecutive days (Day 1 to 3), every 21 days, for a maximum of 5 cycles.

Treatment with lenvatinib will continue in 21-day cycles after chemotherapy is discontinued, until disease progression, development of unacceptable toxicity, subject request, withdrawal of consent, or discontinuation of study by the sponsor. In case the study is discontinued by the sponsor, the sponsor will provide study drug (outside the study) for subjects who have not met the criteria for study drug discontinuation.

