#### 9.4.7.3 Permitted Concomitant Treatment/Procedures

The following concomitant treatments/procedures are allowed:

- a. Removal of existing (not new) osteosarcoma lesion (eg, surgical, radiofrequency ablation, cryotherapy, thermoablation, stereotactic radiotherapy, etc.) after completion of the Week 18 tumor assessment. Subjects may continue study treatment after protocol permissible surgery in the presence of clinical benefit, with Sponsor approval.
- b. Palliative radiotherapy is allowed for  $\leq 2$  significantly symptomatic nontarget lesions.

If a subject receiving treatment with lenvatinib requires surgery during the study, the stop time and restart time of lenvatinib should be as follows:

- For minor procedures: stop lenvatinib at least 2 days before the procedure and restart it at least 2 days after, once there is evidence of adequate healing and no risk of bleeding.
- For major procedures: stop lenvatinib at least 1 week (5 half-lives) prior to surgery and then restart it at least 2 weeks after, once there is evidence of adequate healing and no risk of bleeding.

Any additional procedural or subject specific particularities should be discussed with the investigator and the sponsor.

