#### **9.5.1.3 Pharmacokinetic, Pharmacodynamic, and Other Biomarker Assessments**

##### **9.5.1.3.1 PHARMACOKINETIC ASSESSMENTS**

In order to ensure patient safety and not exceed the maximum allowable volume for blood collections, pharmacokinetic sampling should not be performed for any subject with a body weight <13 kg. Blood samples (2 mL each) will be collected from all subjects from Arm A only at the time points shown in [Table 3](#). Pharmacokinetic blood samples will also be drawn pretreatment on the day of tumor assessment as described in the [Table 3](#). Actual time and

date of PK blood collection as well as time of drug administration will be recorded on the appropriate page of the CRF. Exposure parameters such as area under the concentration  $\times$  time curve (AUC) will be derived from posterior estimates of the PK parameters from the final population PK model. For the time points shown in Table 3, subjects or their parents will be instructed not to take the dose of lenvatinib prior to arriving at the study site.

Lenvatinib capsule administration will be recorded in the eCRF. The Cycle 1 Day 1 and Day 15 doses of lenvatinib will be administered at the study site at approximately the same time of day in order to accommodate PK sample collection timing. Instructions for the collection, handling, and shipping procedures of PK samples will be provided in a separate Laboratory Manual.

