**Table 5 Schedule of Assessments in Study E7080-G000-230 – Randomization Phase**

Phase	Prerandomization		Randomization a (All cycles are 21 days in duration)																		
	Screening b	Baseline c	Treatment d																Off-Tx	Follow-up	
Period	Visit	1	2	3	4	5	6	7	8	9	10	11	12	13	14	15	16	17	18+		
Visit			Cycle 1			Cycle 2			Cycle 3			Cycle 4			Cycle 5			Cycle 6-X			
Day	-28 to -2	-1	1	8	15	1	8	15	1	8	15	1	8	15	1	8	15	1			
Procedures/Assessments			Arm A: Combination of lenvatinib (QD) + ifosfamide + etoposide (Days 1-3 of Cycles 1-5 only) [based on BSA calculations at Day 1 of each Cycle]; after Cycle 5 subjects will receive lenvatinib alone. Arm B: Ifosfamide + etoposide (Days 1-3 of Cycles 1-5 only) [based on BSA calculations at Day 1 of each Cycle]																		
Study treatment o			X																		
Palatability Questionnaire p			X																		
Tumor assessments: CT/MRI q	X		CT chest and CT/MRI of other areas of known disease at Screening plus any areas of newly suspected disease should be performed every 6±1 week after the date of randomization or sooner if clinically indicated until Week 18±1 week, then every 9±1 weeks until Week 54±1 week. Thereafter, to be performed every 12±2 weeks until documentation of PD.																	X q	
Brain CT/MRI r	X		Brain scans will be performed at screening as clinically indicated, and thereafter during treatment if clinically indicated. For subjects with protocol-eligible, treated brain metastases at Screening, brain scans should be performed at all tumor assessment time points.																		
Height s		X	X												X					X	X
Tanner Stage t		X																			X
Proximal tibial growth plate x-ray s		X																			X
Dental examination s		X	X as per standard of care or at least annually																		X
HRQoL u		X	HRQoL will be collected on C2D1, C3D1, Week 18, C8D1, and C18D1.																		X u
Pharmacodynamic biomarkers v		X			X	X									X					X	
Archival tumor block or slides w			X																		
Survival x															X						X

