- l. Clinical chemistry and hematology results must be reviewed by the investigator prior to administration of study drug on C1D1 and within 48 hours after administering any study drug for all subsequent cycles. Electrolytes such as potassium, calcium, and magnesium should be monitored and abnormalities, when considered clinically significant, should be corrected in all participants before starting treatment. Scheduled assessments may be performed within 72 hours prior to the visit. If  $\geq$ Grade 3 hematologic or clinical chemistry toxicity, repeat laboratory test and AEs assessment at least every 3 days (until improvement to <Grade 3). TSH should be assessed for all subjects. For sites in Germany: HIV and Hepatitis B/C tests are required during Screening.
- m. Urine dipstick testing should be performed at Screening, Baseline, C1D15, C2D1, C2D15, and Day 1 of every subsequent cycle, or more frequently as clinically indicated, and at the Off-treatment Visit. For subjects with a history of proteinuria  $\geq$ 2+, urine dipstick testing should be performed until the results have been 1+ or negative for 2 treatment cycles. If a new event of proteinuria  $\geq$ 2+ occurs, refer to [Section 9.4.1.1.4](#) for further management guidelines. Urine glucose should be performed as part of the urine dipstick.
- n. Sampling (one 2 mL sample per time point) for PK analysis of lenvatinib will be performed (in subjects in Arm A only) on Cycle 1 Day 1 at 0.5 to 4 hours and 6 to 10 hours postdose, on Cycle 1 Day 15 at predose, 0.5 to 4 hours and 6 to 10 hours postdose, and on Cycle 2 Day 1 at predose. All predose samples are to be drawn approximately 24 hours following the dose administered on the previous day. If dose interruption is necessary at these time points, please contact the sponsor. Pharmacokinetic sampling should not be performed for any subject with a body weight <13 kg (please see [Section 9.5.1.3.1](#)).

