#### 9.7.1.1.2 SECONDARY ENDPOINTS

- Progression-free survival rate at 4 months (PFS-4m) by IIR is defined as the percentage of subjects who are alive and without PD at 4 months from the randomization date as determined by IIR of radiological imaging using RECIST 1.1. The PFS-4m rate is estimated using the Kaplan-Meier (K-M) method.
- Progression-free survival rate at 1 year (PFS-1y rate) by IIR is defined as the percentage of subjects who are alive and without PD at 1 year from the randomization date as determined by IIR of radiological imaging using RECIST 1.1. The PFS-1y rate is estimated using the K-M method.
- Overall survival (OS) is defined as the time from the date of randomization to the date of death from any cause. Subjects who are lost to follow-up and those who are alive at the date of data cutoff for the primary analysis, will be censored at the date the subject was last known to be alive, or date of data cutoff for the primary analysis, whichever occurs first. Overall survival rate at 1 year will be estimated using the K-M method.
- Objective response rate by IIR at 4 months (ORR-4m) is defined as the proportion of subjects who have best overall response of complete response (CR) or partial response (PR) as determined by IIR using RECIST 1.1 within the first 4 months.
- Objective response rate (ORR) by IIR is defined as the proportion of subjects who have best overall response of complete response (CR) or partial response (PR) as determined by IIR using RECIST 1.1.
- Safety will be assessed summarising the incidence of TEAEs and SAEs together with all other safety parameters.
- Assessment of population-based PK parameters of lenvatinib.
- Score changes from baseline for all PedsQL scales including Generic Core Scales and Cancer Module. Scores will be calculated for total generic score, total cancer score, each physical function subscale including physical health, psychosocial health, emotional function, social function, school/work function in the Generic Core Scales, and each subscales in the cancer module.

- Palatability and acceptability of the suspension formulation of lenvatinib in subjects receiving the suspension formulation in the study will be assessed using the Palatability Questionnaire (see [Appendix 4](#)).

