#### 9.7.1.7 Pharmacokinetic, Pharmacodynamic, and Other Biomarker Analyses

##### 9.7.1.7.1 PHARMACOKINETIC ANALYSES

Lenvatinib concentration versus time data will be tabulated and summarized and graphically presented.

Lenvatinib data from Arm A of the study will be pooled with available data from other studies and subjected to population PK analysis. The PK model will be parameterized in terms of clearance and volume of distribution. Details of the population PK analysis will be provided in a separate analysis plan.

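### The lenvatinib PK schedule has no steady-state sample on the chemotherapy days, so it is nearly blind to a transient Day 1-3 effect, and the text mentions PK samples that the sampling table does not list

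*Protocol*

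**What the plan says.** The objective (Protocol Section 8.2, item 7) is to "Characterize the pharmacokinetics (PK) of lenvatinib, when administered in combination with ifosfamide and etoposide". The matching endpoint in Section 9.7.1.1.2 is "Assessment of population-based PK parameters of lenvatinib". Section 9.7.1.7.1 gives the method: "Lenvatinib data from Arm A of the study will be pooled with available data from other studies and subjected to population PK analysis". The model is in clearance and volume of distribution, and Section 9.5.1.3.1 derives AUC from it.

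In Arm A, lenvatinib is taken daily. Under Section 9.4.1, ifosfamide and etoposide are each given "IV, for 3 consecutive days (Day 1 to 3), every 21 days, for a maximum of 5 cycles". Table 5 agrees: "Combination of lenvatinib (QD) + ifosfamide + etoposide (Days 1-3 of Cycles 1-5 only").

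Table 3, Table 5 footnote n and the blood-volume table in Appendix 11 (Germany) list the same six PK samples:

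- Cycle 1 Day 1: two postdose samples, at 0.5-4 h and 6-10 h.
- "Cycle 1 Day 15 at predose, 0.5 to 4 hours and 6 to 10 hours postdose, and on Cycle 2 Day 1 at predose".

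Predose means about 24 hours after the previous day's lenvatinib dose.

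Section 9.5.1.3.1 adds a further set: "Pharmacokinetic blood samples will also be drawn pretreatment on the day of tumor assessment as described in the" table of sampling times. That table has no tumor-assessment entry.

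**The concern.** What sets lenvatinib PK in combination apart from lenvatinib PK in general is the time when all three drugs are being given. That is Days 1-3 of Cycles 1 to 5. The schedule touches this time only on Cycle 1 Day 1, after the first lenvatinib dose and for no more than 10 hours. That is a short stretch from which to learn about clearance, the parameter from which exposure is derived.

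If chemotherapy changed lenvatinib clearance for a few days and the change then wore off, the samples at steady state would miss it. A report under objective 7 could then describe unchanged lenvatinib exposure although nothing had been measured at steady state while chemotherapy was running.

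The second problem is operational. A site that follows the Section 9.5.1.3.1 text draws PK samples on tumor-assessment days, and a site that follows Table 3 does not. The extra draws are also missing from the blood-volume count.

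**Working it through.** **1. Count and volume.** Table 3 and footnote n give 2 (Cycle 1 Day 1) + 3 (Cycle 1 Day 15) + 1 (Cycle 2 Day 1) = 6 samples, and 6 x 2 mL = 12 mL. This reproduces the Appendix 11 figures of six samples and 12 mL, which leave no room for tumor-assessment samples.

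**2. Half-life.** The PK sections give none. Section 9.4.7.3 says to "stop lenvatinib at least 1 week (5 half-lives) prior to surgery". Reading one week as five half-lives gives 168 h / 5 = 33.6 h (1.4 days). This is an inference from a surgical hold, so 20 h is run as well.

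**3. Calendar (nominal days, no delay).** Chemotherapy falls on study days 1-3, 22-24, 43-45, 64-66 and 85-87. Predose fraction of steady state = 1 - 2^(-(day - 1)/1.4).

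- Cycle 1 Day 1 (day 1): a chemotherapy day, but 0% of steady state before the dose. Sampling ends at 10 h, and 10/33.6 = 0.3 of a half-life.
- Cycle 1 Day 15 (day 15): 15 - 3 = 12 days after chemotherapy; 1 - 2^(-10) = 99.9% of steady state.
- Cycle 2 Day 1 predose (day 22): 22 - 3 = 19 days after chemotherapy; 1 - 2^(-15), about 100%. Chemotherapy resumes that day, but the trough reflects the preceding 24 h, which are free of it.

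Steady-state samples within the chemotherapy days: 0 of 6.

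**4. Sensitivity to an effect.** One-compartment model with doses every 24 h, absorption rate 1/h and k0 = ln 2 / half-life. The elimination rate is k0 x 0.7 or k0 x 1.3 from each cycle's Day 1 dose, either for 72 h only, or for 72 h and then fading with a 7-day half-life. The size and both durations of the effect are assumptions. Entries are percent change in concentration against no effect; where two signs appear, the first is for reduced clearance.

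| Sample | 33.6 h, effect 72 h only | 20 h, effect 72 h only | 33.6 h, effect fading |
|---|---|---|---|
| C1D1, 0.5-4 h | 0.2 to 1.9 | 0.3 to 3.2 | as column 1 |
| C1D1, 6-10 h | 3.0 to 5.7 | 5.0 to 9.8 | as column 1 |
| C1D15 predose | 0.1 | 0 | +19 / -14 |
| C2D1 predose | 0 | 0 | +9 / -7 |
| C2D2 predose (not scheduled) | +16 / -14 | +28 / -22 | +22 / -17 |
| C2D3 predose (not scheduled) | +27 / -21 | +43 / -29 | +31 / -23 |

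The C1D1 rows give absolute sizes over the window. With an effect that never fades (33.6 h), C1D15 predose changes by +53% / -29%.

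**5. Would the tumor-assessment samples help?** Weeks 6 and 12 fall nominally on days 43 and 85, which are Day 1 of Cycles 3 and 5. Drawn before treatment, they would again be troughs taken before that cycle's chemotherapy.

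**The case against.** The strongest reply is that this is ordinary sparse pediatric sampling feeding a pooled population model, and that the protocol promises nothing finer. Objective 7 asks for characterisation. No interaction test, infusion-day contrast or comparison with monotherapy is planned. That stands, and it rules out three stronger readings that a reader might infer.

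- *The samples cannot answer objective 7.* Two samples per subject are taken on a day of actual co-administration, and the other four come from subjects on the combination regimen.
- *The steady-state samples measure lenvatinib alone.* With an effect that fades over a week or persists, Cycle 1 Day 15 moves by 14% or more at predose. The zeros in the table come from assuming that the effect ends at 72 h.
- *The analysis would find no difference from monotherapy whatever the truth.* The protocol states no such comparison. It does not identify the pooled studies as monotherapy, and Study 207 had a combination cohort (Section 7.3.1).

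It is also fair that the documents give no basis for a 30% change caused by ifosfamide or etoposide. Section 9.4.7.1 reports lenvatinib exposure changes up to about 31% with other drugs and does not regard them as clinically meaningful. The half-life is likewise inferred, not reported.

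What the reply does not remove is the gap itself. No assumption about effect size puts a steady-state sample on a chemotherapy day. Pooling adds no such sample from this trial. Nor does the reply resolve the conflict between Section 9.5.1.3.1 and Table 3.

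**Conclusion.** The point holds in a limited form. The six scheduled samples can describe lenvatinib PK over the combination regimen and would carry a signal of any chemotherapy effect lasting about two weeks or more. They are nearly blind to an effect confined to Days 1-3 at steady state. For a 30% clearance change over 72 h, the largest shift in any scheduled sample is about 6% (10% at a 20 h half-life), against 21-27% (29-43%) at a Cycle 2 Day 3 predose sample.

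These sizes rest on a one-compartment model, an assumed effect, nominal visit days and, for 33.6 h, the inferred half-life. The calendar finding, 0 of 6, needs only the nominal days and the half-life, and is the same at 20 h.

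This affects a secondary objective only, and the change is a cheap improvement. The mismatch between Section 9.5.1.3.1 and Table 3 is a plain contradiction that depends on no model.

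**What to change.** 1. Replace the Cycle 2 Day 1 predose sample with a sample drawn before the lenvatinib dose on the second or third day of the Cycle 2 chemotherapy actually given. Tie it to the infusion and not to the nominal cycle day: Section 9.1.2.1 counts cycles continuously and lets chemotherapy be delayed, so a sample fixed to a cycle day could miss it. Table 5 has no column for these days, so the footnote must carry the rule.
2. Record infusion start and stop times in that cycle.
3. Amend Table 3, Table 5 footnote n and the Appendix 11 blood-volume table to match.
4. Reconcile Section 9.5.1.3.1 with Table 3. Either delete the tumor-assessment sentence, or enter those samples in Table 3, Table 5 and the volume table at 2 mL each.

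Cost: items 1 to 3 keep six samples and 12 mL, and use a day when the subject attends for infusion anyway. Cycle 1 Day 15 predose remains as the trough away from chemotherapy, so each subject gives a within-subject comparison. What is lost is a second such trough, which largely duplicates Day 15. In the cases computed, the new sample responds at least as strongly as the one that it replaces.

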**Table 5 Schedule of Assessments in Study E7080-G000-230 – Randomization Phase**

Phase	Prerandomization		Randomization a (All cycles are 21 days in duration)																	
	Screening b	Baseline c	Treatment d																Off-Tx	Follow-up
Period	1	2	3	4	5	6	7	8	9	10	11	12	13	14	15	16	17	18+		
Visit	1	2	3	4	5	6	7	8	9	10	11	12	13	14	15	16	17	18+		
Cycle			Cycle 1			Cycle 2			Cycle 3			Cycle 4			Cycle 5			Cycle 6-X		
Day	-28 to -2	-1	1	8	15	1	8	15	1	8	15	1	8	15	1	8	15	1		
Procedures/Assessments																				

- o. Subjects randomized to Arm A will continue to receive lenvatinib only after completion of 5 cycles with lenvatinib+ifosfamide+etoposide until progressive disease, unacceptable toxicity, subject request, study termination by the sponsor, subject noncompliance with safety or efficacy assessments, or withdrawal of consent. Subjects randomized to Arm B will be off-treatment after 5 cycles of ifosfamide+etoposide.
- p. All subjects who receive suspension formulation, with the exception of subjects using a nasogastric or gastrostomy tube, must complete the Palatability Questionnaire on C1D1 (or the subsequent visit). If the subject is unable to complete the questionnaire this must be done by their parents or their legal guardian.
- q. **Screening:** Tumor assessments of the chest, abdomen, pelvis, and other areas of known disease or newly suspected disease should be performed within 28 days prior to C1D1. Scans of the abdomen, pelvis, and other areas of the body may be done with MRI instead of CT, but evaluation of the chest should be done with CT. CT scans should be performed with iodinated IV contrast and MRI scans should be performed with IV gadolinium chelate.
- Treatment Phase:** Tumor assessments of the chest, and other areas of known disease at Screening or newly suspected disease should be performed every 6±1 weeks from the date of randomization until Week 18±1 week, then every 9±1 weeks until Week 54±1 week, and thereafter, every 12±2 weeks until documentation of PD during the Treatment Phase (or sooner if there is evidence of progressive disease) and should utilize the same methodology (CT or MRI) and scan acquisition techniques (including use or nonuse of IV contrast) as was used for the screening assessments. Tumor response will be assessed according to RECIST 1.1. Any CR or PR must be confirmed not less than 4 weeks following the initial achievement of the response. **Off-Treatment:** Tumor assessments at the Off-Treatment Visit (within 1 week of the Off-treatment Visit) are only necessary for subjects who discontinue study treatment without disease progression, if more than 4 weeks have passed since the previous assessment and if the subject will not continue with follow-up scans.
- Follow-up:** For subjects who discontinue study treatment without disease progression, tumor assessments should continue to be performed according to the schedule: every 6±1 weeks until Week 18±1 week, then every 9±1 weeks until Week 54±1 week, thereafter, to be performed every 12±2 weeks, until documentation of progression or start of a new anticancer agent.
- r. Brain CT with contrast or MRI pre- and post- gadolinium contrast will be performed at the Screening Visit as clinically indicated, and thereafter during treatment as clinically indicated. For subjects with protocol-eligible treated brain metastases, brain CT/MRI will be performed at all tumor assessment time points.
- s. Height will be assessed at the Baseline Visit, Day 1 of every 4 cycles during the Treatment Phase, at the Off-treatment Visit and every 3 months during the Post-treatment Follow-up. Assessment of height in Post-treatment Follow-up is not required once pubertal development is complete. Proximal tibial growth plate x-rays should be conducted for subjects aged <18 years at baseline and at the Off-treatment Visit. If the growth plates are closed at baseline

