#### **Sample Size Rationale**

A total sample size of 72 subjects is estimated for the primary efficacy endpoint of PFS. Assuming a hazard ratio of 0.4 (median PFS of 3.5 and 8.75 months for the control arm and the test arm, respectively), a one-sided type 1 error rate of 0.025, and power of 80%, 38 PFS events are required for the primary analysis. The total sample size of 72 subjects is estimated to achieve 38 PFS events assuming the analysis occurs approximately 32 months after the first subject is randomized (assuming a 20-month enrollment period), and accounts for a dropout rate of up to 40%.

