#### 9.1.2.1 Treatment Period

The Treatment Period for each subject will begin at the time of randomization and will end at the completion of the Off-Treatment Visit which will occur within 30 days after the final dose of study treatment.

Subjects will receive study treatment as continuous 21-day cycles in both treatment arms. Treatment cycles will be counted continuously regardless of dose interruptions. If chemotherapy administration is precluded on Day 1 of a treatment cycle, the subject may resume treatment once recovered at the discretion of investigator. Subsequent chemotherapy will be administered every 21 ( $\pm 1$ ) days starting from the timepoint it was resumed. Subjects will undergo safety and efficacy assessments as defined in the Schedule of Procedures/Assessments ([Table 5](#)). Subjects randomized to Arm A will continue to receive lenvatinib until disease progression (PD) confirmed by IIR, development of unacceptable toxicity, subject request, withdrawal of consent, or study termination by the sponsor, whichever occurs first.

Disease progression (PD) must be confirmed by IIR prior to the investigator discontinuing study treatment for a subject. In situations where the investigator judges that alternative treatments must be instituted immediately for a subject's safety, study drugs may be discontinued without waiting for IIR confirmation of radiographic evidence of PD. If possible, before discontinuation of the subject from the study, the investigator should consult with the sponsor.

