#### 9.1.2.2 Follow-Up Period

The Follow-up Period begins the day after the Off-Treatment Visit and will continue for up to 2 years after end of treatment for a subject, unless the subject withdraws consent or the sponsor terminates the study.

Subjects may at any time withdraw consent for further study participation. No further data will be collected on subjects once consent has been withdrawn, however, an investigator may consult public records to establish survival status if permitted by local regulations.

All adverse events (AEs), including serious adverse events (SAEs), will be captured for 30 days after the last dose of study drug.

All subjects who end study treatment without IIR confirmed PD, will continue to undergo tumor assessments every 6 weeks until Week 18, then every 9 weeks until Week 54, thereafter, every 12 weeks until IIR confirmation of radiographic evidence of PD as described in the tumor assessments in the assessment schedule, or until another anticancer therapy is initiated.

Subjects in both Arm A and Arm B will be followed for survival every 12 weeks ( $\pm 1$  week) and all subsequent anticancer treatments received will be recorded. Subjects who are being followed for survival at the time of data cutoff for the primary analysis (ie, at the end of the

Randomization Phase) will continue to be followed for survival during the Follow-up Period of the Extension Phase.

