### **During Post-treatment Follow-up**

Subjects who discontinue treatment without PD will have tumor assessments performed as per the appropriate tumor assessment schedule) or sooner if clinically indicated, for documented PD or until another anticancer therapy is initiated, whichever occurs first.

After data cutoff for the primary analysis, tumor assessments may be performed as clinically indicated as per the institutional guidelines (but no less frequently than every 12 weeks), following the prevailing local standard of care. All subjects will be followed for survival for up to 2 years after end of treatment, unless the study is terminated by the sponsor, or the subject discontinues due to withdrawal of consent, or is lost to follow-up.

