#### 9.5.5      **Completion/Discontinuation of Subjects**

A subject (or subject's parent or guardian) may elect to discontinue study drug at any time for safety, medical, or personal reasons. Subjects who choose to discontinue study drug prior to PD will be followed in the post-study treatment follow-up period and continue to undergo regularly scheduled disease assessment until documentation of PD or start of an alternative anticancer treatment. All subjects who discontinue study drug will be followed for OS and all post progression cancer treatments administered will be recorded. Subjects may at any time withdraw consent for further study participation. No further data will be collected on subjects once consent has been withdrawn. All subjects who discontinue the study are to complete the study's early discontinuation procedures indicated in the Schedule of Assessments ([Table 5](#) and [Table 6](#)).

The investigator will promptly explain to the subject (or subject's parent or guardian) involved that the study will be discontinued for that subject and provide appropriate medical treatment and other necessary measures for the subject. A subject who has ceased to return for visits will be followed up by mail, phone, or other means to gather information such as the reason for failure to return, the status of treatment compliance, the presence or absence of AEs, and clinical courses of signs and symptoms.

Subjects who discontinue early from the study will be discontinued for 1 of these primary reasons: AE(s), lost to follow-up, subject choice, progression of disease, withdrawal of consent, pregnancy, study terminated by sponsor, or administrative/other. In addition to the primary reason, the subject may indicate 1 or more secondary reason(s) for discontinuation. Study disposition information will be collected on the Subject Disposition CRF.

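### The protocol has two rules for when post-treatment tumor scans stop: at IIR-confirmed progression, or at documented progression with no assessor named, so IIR PFS events could be lost

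*Protocol*

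**What the plan says.** PFS is defined by IIR (Section 9.7.1.1.1), and the data cutoff falls at about 38 IIR-determined events (Sections 9.1.2 and 9.7.1.6). Two rules govern how long scans continue.

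- **Rule 1, IIR-confirmed progression.** Section 9.1.2.2: "All subjects who end study treatment without IIR confirmed PD, will continue to undergo tumor assessments every 6 weeks until Week 18", then on the later schedule until IIR confirms progression or another anticancer therapy starts. The Synopsis (Study Design) agrees.
- **Rule 2, documented progression, assessor not named.** Table 5 footnote q, on follow-up: "For subjects who discontinue study treatment without disease progression, tumor assessments should continue to be performed according to the schedule", until progression is documented or a new anticancer agent starts. Section 9.5.1.2.1, post-treatment follow-up: "Subjects who discontinue treatment without PD will have tumor assessments performed", again to documented PD. Section 9.5.5: subjects who choose to stop before PD "continue to undergo regularly scheduled disease assessment until documentation of PD or start of an alternative anticancer treatment". Section 9.3.3 and the Synopsis (Efficacy Assessments) read the same way.

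Rule 1 also refers the site to the assessment schedule for the scans. That schedule is Table 5, which carries Rule 2.

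A separate check sits in Section 9.1.2.1 and is repeated in Section 9.5.1.2.1: "Disease progression (PD) must be confirmed by IIR prior to the investigator discontinuing study treatment for a subject". An exception applies when other treatment is needed urgently. Table 5 footnote o adds: "Subjects randomized to Arm B will be off-treatment after 5 cycles of ifosfamide+etoposide".

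**The concern.** Investigators know the treatment arm and record their own response assessment at every time point (Sections 9.4.6 and 9.5.1.2.1). A site that follows Table 5 can reasonably take its own recorded progression as the end of scanning. If IIR has not agreed, no later scan exists on which IIR could call the event, and the subject is censored when progression is probably close. That is informative censoring in the primary endpoint. The SAP cannot repair it, because scans that were never taken cannot be read later.

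The exposure may differ by arm. The check before stopping treatment works only while there is treatment to stop. Arm A continues lenvatinib until IIR-confirmed progression, whereas Arm B is off treatment after five cycles, so from then on the check has nothing to act on. The stakes are lost IIR events, a later cutoff, and a hazard ratio pulled toward 1 if the loss falls mainly on the control arm.

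**Working it through.** **1. The plan's own figure.** Inputs from the Sample Size Rationale and Section 9.7.2: medians 3.5 and 8.75 months (hazard ratio 0.4), 72 subjects randomized 1:1, 20-month enrollment, analysis at month 32, up to 40% dropout, and "a one-sided type 1 error rate of 0.025, and power of 80%, 38 PFS events are required for the primary analysis".

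- Schoenfeld: D = 4(1.960 + 0.842)² / (ln 0.4)² = 37.39, rounded up to 38. Power at 38 events is Φ(√38/2 × 0.916 − 1.960) = 80.6%.
- Exponential PFS with uniform accrual gives event probabilities of 0.977 (Arm B) and 0.806 (Arm A) by month 32. Events: 36 × 0.977 + 36 × 0.806 = 35.2 + 29.0 = 64.2, and 64.2 × 0.60 = 38.5. N = 38 / (0.8915 × 0.60) = 71.0, against 72 stated.

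Both figures reproduce.

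**2. How much of each arm lies beyond Cycle 5.** Five 21-day cycles are 105 days, or 3.45 months.

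- Arm B event-free: 2^(−3.45/3.5) = 50.5%, about 18 of 36. Arm A: 2^(−3.45/8.75) = 76.1%.
- Events after Week 15, before dropout: Arm B 36 × (0.977 − 0.495) = 17.3 of 35.2; Arm A 36 × (0.806 − 0.239) = 20.4 of 29.0.

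So about half of the control events occur while Arm B is still on treatment and under the IIR check.

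**3. If a share f of post-Week-15 IIR events is lost (assumed; no source in the documents).** The average hazard ratio weights ln 0.4 by the events before Week 15 and ln[0.4/(1 − f)] by those after, with the loss in Arm B only. Events before Week 15 are 36 × (0.495 + 0.239) = 26.4. For f = 20%, Arm B loses 3.5 events, leaving 34.3 after Week 15, and exp[(26.4 × ln 0.4 + 34.3 × ln 0.5)/60.7] = 0.45.

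| f | Arm B events lost, before dropout (× 0.6) | Events by month 32, Arm B loss only | Average HR | Power at 38 events | Arm A events also lost if f is equal (× 0.6) | Events by month 32, equal loss |
|---|---|---|---|---|---|---|
| 10% | 1.7 (1.0) | 37.5 | 0.43 | 75% | 1.2 | 36.2 |
| 20% | 3.5 (2.1) | 36.4 | 0.45 | 68% | 2.4 | 34.0 |
| 30% | 5.2 (3.1) | 35.4 | 0.49 | 60% | 3.7 | 31.7 |

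At equal f, Arm A loses slightly more events than Arm B. Both post-Week-15 hazards are then scaled by the same factor (1 − f), so the ratio stays near 0.4 and the cost is events and time.

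**4. Simulation on the protocol's scan weeks.** There are 36 subjects per arm, exponential PFS and no dropout. Scans fall at Weeks 6, 12, 18, 27, 36, 45 and 54, then every 12 weeks. In 10% / 20% / 30% of Arm B subjects, scanning stops one scan before the IIR event when that earlier scan falls after Day 105; nobody in Arm A is affected.

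- Control events lost: about 1.5 / 3 / 5. Repeat runs put the last figure at 4.4.
- Mean hazard ratio: from 0.44 to about 0.45 / 0.46 / 0.49.
- With no true effect: from about 1.0 to 1.02 / 1.06 / 1.10.

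The start is 0.44, not 0.40, because dating progression at scheduled scans creates many ties; a rerun reproduced it with Breslow tie handling. The shift is the quantity of interest.

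**The case against.** The strongest reply is that Rule 1 already binds both arms. Section 9.1.2.2 and the Synopsis cover all subjects who end treatment, including Arm B subjects who simply finish chemotherapy. Figure 1 note c requires IIR confirmation before the Extension Phase without naming an arm. Section 9.3.3 says confirmation is no longer required after the cutoff, which implies that it was required before. Section 9.1.4 makes IIR-confirmed progression a condition of crossover before the Extension Phase, so sites have a reason to seek it in Arm B. All scans go to the imaging core laboratory. This stands, and it rules out saying that only Arm A is held to IIR confirmation. It does not remove the conflict: crossover is optional and conditional, and the core laboratory can read only scans that were taken.

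Two stronger readings are tempting, and the documents support neither.

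- A reader might infer that Table 5 stops scans at investigator-documented progression. It does not say so. The endpoint definition itself speaks of documentation as determined by IIR, so the wording is ambiguous, and the ambiguity is the defect.
- A reader might infer that events will be lost mainly in the control arm. The protocol gives no rate of disagreement between investigator and IIR. The arm-specific result in the simulation comes from applying the loss to Arm B alone. Arm A is not immune: subjects who stop for toxicity or by request fall under the same footnote, and the urgent-treatment exception covers both arms. New anticancer therapy ends scans under either rule.

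**Conclusion.** The contradiction is real and sits in the current text. It concerns the scans that determine the primary endpoint and trigger the primary analysis. IIR events could be lost to informative censoring in either arm, possibly more often in Arm B after Cycle 5, with Section 9.1.2.2 and the crossover condition as partial offsets.

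The size is conditional. If 10% to 30% of Arm B subjects were affected after Week 15 and none in Arm A, about 1.5 to 5 control events would be lost and the hazard ratio would move from about 0.44 to 0.45–0.49. This rests on exponential PFS at the planned medians and on a discordance range and one-scan lead that are assumed. The bias runs against lenvatinib, so it costs power and distorts the estimate without raising the false-positive risk. With 80.6% power at 38 events, the margin is thin.

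**What to change.** Reconcile the passages. For the Randomization Phase, use the Section 9.1.2.2 rule (scans continue until IIR confirms progression or another anticancer therapy starts) in Table 5 footnote q, Sections 9.3.3, 9.5.1.2.1 and 9.5.5, and the Synopsis (Efficacy Assessments). State that it applies to both arms, on or off study treatment, and that scheduled scans continue when IIR does not confirm an investigator's call of progression.

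The cost is a wording change and a few extra scheduled scans. The scans already go to the imaging core laboratory, and the sample size and event target do not change.
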